## 12b. Statistical methods

As a reminder, the sample-size is designed to support a factor analysis for the hand-hygiene component of the project. The surface cleaning component of the project will only be analyzed using descriptive and exploratory methods.

Software: The data will be analysed using the most recently available copies of SPSS and SPSS: AMOS.

Descriptive: Frequencies, percentages, averages and confidence intervals will be used to describe the participants' responses and demographics.

Internal Consistency: Cronbach's alphas will be calculated. Items will be removed as necessary to achieve an alpha coefficient of 0.70 or above within each domain; those coefficients as low as 0.65 will be tolerated if necessary to retain the planned model.

[figure not shown]
Confirmatory Factor Analyses (CFA) - Objective 4: CFA will be performed to test whether the data from the items fit within the pre-determined components.

The first models (the primary analyses) will be conducted with the data from all the countries and then additional models (the secondary analyses) will be conducted with each country.

The models will be specified in AMOS and tested for goodness of fit using three indices: (a) absolute fit (based on a Chi-squared to degrees of freedom ratio, less than 2; ), (b) parsimony (based on Root Mean Square Error of Approximation (RMSEA) of close to or less than 0.06), and comparative fit (based on an index 'close to' 0.95; ). The models may be revised until the desired measures of fit are obtained.

Figure will be created to describe the final models' structure. An example of a figure like this with only 2 determinates appears below (Figure 2):

Figure 2. Example of a CFA model

Regression analyses - Objective 5: Multiple regression analysis will be conducted, overall and for each country. The predictors will be participants' average responses to each behavioural determinate, and the outcome will be participants' average responses to the confidence items. An alpha value of 0.05 will be used to assess each predictors' contribution to the overall model.

Exploratory Analyses - Objective 6: The participants' individual differences will be compared using graphical analyses (bar charts with error bars) and statistical tests (e.g., ANOVAs). Their content is not further specified within this protocol.

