Appendix A also includes three self-confidence items.

The first item regards participants' confidence about how often their children clean their hands when they are present, 0% to 100% of the time. The second item regards participants' confidence about how often their children clean their hands when they are not present, 0% to 100% of the time. The third item regards participants' confidence about how often they clean their own hands, 0% to 100% of the time.

*Translation.*

After creating the initial items in the English language, the research team will ask OpinionHealth to translate them. The same process will occur for the information/consent sheet. The translation process will proceed as describe in Table 1.

Table 1. Translation process

Step	Action
1	The research team will provide OpinionHealth with the initial items.
2	OpinionHealth will translate the items into the non-English language(s)
3	OpinionHealth will back-translate the items to English.
4	OpinionHealth will provide the research team with copies of the translated and back-translated items.
5	The research team will check to be sure that the items' intended meanings have not been lost in translation. If items' meaning are lost, the translation process will be repeated with those items.

---

Opinion is a reputable survey company located in the United Kingdom experienced in conducting online surveys in line with all UK and EU regulations and Market Research Society's Code of Conduct, e.g., GDPR. For more information, a link to Opinion Health's website is provided here:  
[http://opinionhealth.com/about\\_us](http://opinionhealth.com/about_us)

*Active survey.*

OpinionHealth will to recruit participants according to a stratified fashion across countries and demographic characteristics, see Table 2.

Table 2. Participants stratified characteristic

Country	Participants
India	375 mums 375 dads 75 teachers
UK	225 mums 225 dads 75 teachers
China	225 mums 225 dads 75 teachers
Australia	225 mums 225 dads 75 teachers
South Africa	225 mums 225 dads 75 teachers
Indonesia	225 mums 225 dads 75 teachers
Saudi Arabia	225 mums 225 dads 75 teachers

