## **12. Statistical Considerations and Data Analysis**

### **12a. Sample size and statistical power**

The sample-size is designed to support a factor analysis and regression analysis for the hand-hygiene component of the project. The surface cleaning component of the project will be analyzed using descriptive and exploratory methods.

The planned sample size is given in Table 2.

As per standard practice, each domain in the final survey will be captured by at least three items. In addition, a general rule of thumb recommends that collecting responses from 10 to 20 participants for each parameter in the hypothesized model with at least 100 participants in each sub-group. Our planned samples size meets these criteria, with the exception of teachers and this limitation will be noted in any published reports.

The exploratory analyses do not have pre-specified hypotheses and so it is not possible to say how many participants would be required. Cohen (1998) recommends having at least 30 participants in each subgroup. Our large sample size should entail having a sufficient number of participants for these exploratory analyses, and the precise number of participants in each will be specified in any publication.

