Intentions / Goals (referred to as: action plans in Dyson et al) (Intentions) A conscious decision to perform a behaviour or a resolve to act in a certain way (Goals) Mental representations of outcomes or end states that an individual wants to achieve	37	H	I intend to keep reminding my children to wash their hands after going to the toilet.	I intend to keep reminding my pupils to wash their hands after going to the toilet.
	38	H	(RS) I do not intend to teach my children to wash their hands.	(RS) I do not intend to teach my pupils to wash their hands.
	39	SD	I intend to regularly disinfect surfaces in my home.	I intend to regularly disinfect surfaces in the classroom .
	40	SD	(RS) I do not intend to regularly disinfect surfaces in my home.	(RS) I do not intend to regularly disinfect surfaces in the classroom .
Emotion A complex reaction pattern, involving experiential, behavioural, and physiological elements, by which the individual attempts to deal with a personally significant matter or event	41	H	(RS) Teaching my children to wash their hands is frustrating.	(RS) Teaching my pupils to wash their hands is frustrating.
	42	H	(RS) Reminding my children to wash their hands is tedious.	(RS) Reminding my pupils to wash their hands is tedious.
	43	H	I enjoy praising my children for washing their hands.	I enjoy praising my pupils for washing their hands.
Environmental context and resources (Any circumstance of a person's situation or environment that discourages or encourages the development of skills and abilities, independence, social competence, and adaptive behaviour)	44	H	(RS) There is not enough time for my children to wash their hands.	(RS) There is not enough time for my pupils to wash their hands.
	45	H	There are practical resources available in my home for my children to wash their hands.	There are practical resources available in my school for my pupils to wash their hands.
	46	H	There are practical resources like running water, available in my home for my children to wash their hands.	There are practical resources like running water, available in my school for my pupils to wash their hands.
	47	SD	(RS) I don't have the time to disinfect surfaces in my home.	(RS) I don't have the time to disinfect surfaces in the classroom .

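### Every planned factor model pools the parent and teacher versions of the survey, so a passing fit cannot by itself support validity for teachers

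*Combined protocol and SAP*

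**What the plan says.** Section 12b defines two sets of data for the confirmatory factor analysis (CFA). The primary set is given by "The first models (the primary analyses) will be conducted with the data from all the countries". For the rest, "additional models (the secondary analyses) will be conducted with each country". The regression is likewise overall and by country, and Cronbach's alpha is calculated within each domain. None of these is split by role, and no test of equivalence between roles is planned. Fit is judged by "absolute fit (based on a Chi-squared to degrees of freedom ratio, less than 2", by "Root Mean Square Error of Approximation (RMSEA) of close to or less than 0.06" and by a comparative fit index near 0.95. Models may be respecified until fit is reached.

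Appendix A has one column of items for parents and another for teachers. Item 45 for parents reads "There are practical resources available in my home for my children to wash their hands"; the teacher version asks about the school and pupils.

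Table 2 (section 11) plans "375 mums 375 dads 75 teachers" in India and "225 mums 225 dads 75 teachers" in each of the other six countries. Section 12a says that the sample meets its size rules "with the exception of teachers and this limitation will be noted in any published reports".

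**The concern.** The abstract presents the survey as measuring parents and teachers, and the primary hypothesis in section 5a covers both without distinction. If the teacher wording does not follow the 11 domains, a model in which about seven of every eight respondents are parents may not show it. A good pooled fit could then be taken as evidence for both versions although it mostly describes one. The country models, which carry the secondary hypothesis, have the same mixture. The limitation disclosed in section 12a concerns the number of teachers. It says nothing about their different wording, or about whether the pooled fit can speak for them.

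**Working it through.** **The plan's own figure.** Section 12a exempts teachers from its minimum of 100 per subgroup. Table 2 agrees: 75 per country is below 100. Pooled over countries, 7 × 75 = 525 teachers exceed it.

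**Teacher share (Table 2).**
- India: 375 + 375 + 75 = 825, of whom teachers are 75/825 = 9.1%.
- Each other country: 225 + 225 + 75 = 525, of whom teachers are 75/525 = 14.3%.
- Total: 825 + 6 × 525 = 3,975. Teachers are 525/3,975 = 13.2% and parents number 3,450.

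**Wording (Appendix A).** There are 11 domains × 3 items = 33 hand-hygiene items. Only item 50 is the same in both columns. Most of the other 32 just replace children with pupils. Item 21 changes the role (parent or teacher), items 45 and 46 the setting (home or school), and item 49 the reference group (family and friends, or colleagues). Items 45 and 46 are two of the three indicators of environmental context and resources.

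**Model size (assuming correlated factors).** 33 loadings + 33 error variances + 55 factor correlations = 121 parameters. The 33 items give 33 × 34/2 = 561 variances and covariances, so df = 561 − 121 = 440.

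**Method.** The documents give no loadings or factor correlations, so these are assumed. Parents follow the 11 domains exactly. Teachers' items have equally strong structure but group into the wrong sets of three. The 11-factor model is fitted by maximum likelihood to (1 − w) × parent covariance + w × teacher covariance, where w is the teacher share and F the minimised discrepancy. Then RMSEA = √(F/440), CFI = 1 − F/F_null, and expected chi-squared/df = 1 + (N − 1)F/440 = 1 + (N − 1) × RMSEA².

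At loading 0.7 and factor correlation 0.5:

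| Data | N | Chi-squared/df | RMSEA | CFI | Criteria met |
|---|---|---|---|---|---|
| Teachers alone | 525 | 4.02 | 0.076 | 0.756 | none |
| Pooled, 13.2% teachers | 3,975 | 1.67 | 0.013 | 0.992 | all three |
| One country, 14.3% teachers | 525 | 1.10 | 0.014 | 0.991 | all three |

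Check on the pooled row: 1 + 3,974 × 0.013² = 1.67.

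Over nine settings (loadings 0.6, 0.7, 0.8; correlations 0.3, 0.5, 0.6):
- Pooled RMSEA is 0.007-0.029 and pooled CFI 0.971-0.997. Both pass every time.
- Pooled chi-squared/df fails in four settings: 4.34, 2.93 and 2.32 at loading 0.8 (correlations 0.3, 0.5, 0.6), and 2.20 at loading 0.7 with correlation 0.3. It passes in the other five (1.17-1.67).
- Country models with N = 525 pass all three criteria in all nine (chi-squared/df at most 1.50).
- Teachers alone have CFI of 0.49-0.88, which fails every time.

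The chi-squared/df results follow from N. A ratio below 2 requires RMSEA below 1/√(N − 1), which is 1/√3,974 = 0.016 for the pooled model but 1/√524 = 0.044 for a country model.

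**Teacher items with no common structure.** The mixture then multiplies every parent covariance by 1 − w, so an 11-factor model still fits exactly, with loadings shrunk by √(1 − w). In 30 simulated 5-point datasets per setting (loadings 0.7 and 0.8, correlations 0.3 and 0.6), the pooled model met all three criteria in every run. Mean pooled alpha fell from 0.71 to 0.66 at loading 0.7, and from 0.81 to 0.76 at loading 0.8, still above the tolerated 0.65. Fitted to teachers alone, such data also pass two criteria (chi-squared/df about 0.9, RMSEA 0). Only alphas and loadings near zero reveal them.

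**Teacher items that split by scoring direction.** In the same simulation, pooled RMSEA passed (0.034-0.050), CFI was 0.91-0.945, and chi-squared/df (5.6-10.9) failed in every run.

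**The case against.** - A reader might infer that a teacher version that fails completely will always pass. The calculations do not support that. Pooled chi-squared/df fails in 4 of 9 settings with regrouped items, and in every run when items split by scoring direction. What remains is that no planned output attributes such a misfit to role, and the respecification rule lets the model be changed until it fits. A high ratio is also not specific to a failing teacher version: role differences in item means (SD 0.5) give 2.7-9.1 even when the teacher structure is sound.
- A reader might infer that the plan claims validity for teachers separately. No sentence does. The claim is only implied, because the survey and hypothesis cover both groups together. Section 12a also promises to report the teacher limitation, which softens the point, but that limitation is about numbers.
- A reader might see two unrelated instruments. Most differences are one-word substitutions, and about four items change in substance.
- A reader might suppose that a school intervention would use the teacher version. The documents say only that the results will inform a future intervention.
- Pooling over roles is inferred, since section 12b never states it. It is the natural reading of a plan that splits by country alone.
- A separate teacher model would have 525/121 = 4.3 respondents per parameter, against the plan's 10 to 20 (1,210 to 2,420 teachers). This stands as a limitation of the remedy.

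**Conclusion.** The concern holds in a limited form. As written, no planned analysis tests the teacher version, and with teachers at 13.2% of the sample the pooled fit can meet the criteria when the teacher items do not follow the 11 domains. For regrouped items, RMSEA and CFI give no warning in any of the nine settings, the N = 525 country models give none on any criterion, and pooled chi-squared/df gives one in four. The pooled result, pass or fail, cannot by itself settle validity for teachers. These sizes rest on assumed loadings and factor correlations, on a correlated 11-factor model, and on assumed forms of teacher misfit. The documents do not show that the teacher version will fail, only that the plan would not establish whether it did.

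**What to change.** In section 12b keep the planned pooled and country models, and add:
1. The same 11-factor CFA fitted separately to parents (planned n = 3,450) and to teachers pooled over countries (planned n = 525), against the same three criteria.
2. Cronbach's alphas and standardised loadings by role, because teacher data without structure would pass chi-squared/df and RMSEA.
3. A two-group AMOS model that tests equal loadings for parents and teachers.

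State that a validity conclusion extends to teachers only if the teacher fit, alphas and loadings support it, and is otherwise limited to parents. Define role by the version answered, since Dem-Q2 and Dem-Q3 allow one person to be both teacher and parent.

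The cost is SAP wording and a few extra AMOS and SPSS runs on data already collected. Teachers need not be removed from the primary or country models, so the study population is unchanged. The teacher model's 4.3 respondents per parameter should be stated as a limitation. It is the same ratio as in the planned country models with N = 525.

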### 1. Abstract

An anonymous online survey measure parents and teachers' barriers and facilitators to influencing children's hand-hygiene and their own surface cleaning. A pilot survey was conducted with participants from the United Kingdom and India, and its results informed what survey items are used in the final survey. The final survey will be conducted with participants from Australia, China, India, Indonesia, Saudi Arabia, South Africa, and the United Kingdom. The data collected will be completely anonymous and there are no sensitive questions. Participants can withdraw simply by closing their browser windows. The primary and secondary analyses focus on the hand-hygiene items, and aim to examine their internal validity. Secondary analyses will look at the surveys external validity. Exploratory analysis will compare participants' responses across countries/regions, and individual differences. The survey results will inform a future school-based intervention and be written up for publication in an academic press acknowledging all collaborating organizations.

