### 4. Objectives

Objective 1. Roll-out a final draft surveys in the different countries/regions.

Objective 2. Conduct a confirmatory factor analyses on the hand-hygiene component of the survey.

Objective 3. Conduct regression analyses to determine whether participants' responses on the hand-hygiene component of the survey predict their self-reported confidence.

Objective 4. Compare participants' responses across each domain, country, and individual difference.

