## 5c. Exploratory Analyses

The exploratory analyses relate to Objective 4.

Participants' hand-hygiene responses across individual difference will be explored using averages and confidence intervals.

Participants' surface disinfecting responses will be assessed as a whole and then compared across countries and individual differences using averages and confidence intervals.

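### Exploratory country comparisons rest on domain averages, but no planned model tests whether the items have equal loadings and intercepts across countries

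*Combined protocol and SAP*

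**What the plan says.** Country comparison is a stated aim. Objective 4 in Section 4 reads "Compare participants' responses across each domain, country, and individual difference", and the abstract says "Exploratory analysis will compare participants' responses across countries/regions, and individual differences". Section 5c gives the metric explicitly for the surface-disinfecting responses, which are to be "compared across countries and individual differences using averages and confidence intervals". For hand hygiene, Section 5c names only individual differences. Section 12b does show how hand-hygiene domains are scored, in its regression paragraph: "The predictors will be participants' average responses to each behavioural determinate".

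For the factor structure, Section 12b makes a model on all countries together the primary analysis, and then "additional models (the secondary analyses) will be conducted with each country". Fit is judged by the chi-squared to degrees-of-freedom ratio, RMSEA and a comparative index. The same section adds: "The models may be revised until the desired measures of fit are obtained". Items may be dropped so that a domain reaches an alpha of 0.70, with 0.65 tolerated to keep the planned model. The section does not say whether removal and revision are done once for all countries or separately.

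The cross-language safeguard is Table 1 in Section 11: translation, back-translation and a check of meaning by the research team. Neither a multi-group model, nor equality of loadings or intercepts, nor differential item functioning is mentioned anywhere.

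**The concern.** Two countries' domain averages can be compared only if people at the same underlying level give the same expected answer to each item. Acceptable fit in each country taken singly shows at most that the items group in the same way. It does not show equal loadings, and it says nothing about intercepts. The pooled model imposes one set of loadings and does not test it. Back-translation addresses meaning, not how readily people endorse an item.

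The results are meant to inform a school-based intervention. An item that is easier to agree with in one country, through wording or response style, would be reported as a difference in barriers. If items were dropped or models revised differently by country, the same domain name could also refer to different item sets.

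**Working it through.** The documents give no SD, effect size, power or test level for country comparisons, so there is no stated figure to reproduce. The size below is an illustration.

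**Inputs from the documents**
- Table 2: 225 + 225 + 75 = 525 planned in each of six countries and 375 + 375 + 75 = 825 in India. The total is 6 × 525 + 825 = 3,975.
- Appendix A, by count: 33 hand-hygiene items, three in each of 11 domains. There are 20 surface items, two in each of ten domains and none for Emotion.

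**Assumptions**
- Domain-average SD of 0.7 on the 1-5 scale (range 0.6 to 0.8), and no true country difference.
- One item's mean differs by 0.25 points in one country.
- Two-sided 0.05 comparison of two countries at full recruitment. Section 12b states 0.05 only for regression predictors.

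**Step 1: would the planned checks see the shift?** Adding a constant c to item X within a country gives var(X + c) = var(X) and cov(X + c, Y) = cov(X, Y). A covariance-based country CFA and alpha therefore do not change. On simulated data with a 0.3 shift, the covariance matrices differed by about 1e-16 and alpha was 0.638 both times. In the pooled data, with equal true levels and one country of 525 shifted, the item's variance grows by p(1 − p)c². With p = 525/3,975 = 0.132 this is 0.132 × 0.868 × 0.0625 = 0.007, which is absorbed as residual variance.

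**Step 2: effect on the comparison.** Bias in the domain average = 0.25/3 = 0.083. SE = SD × √(2/525). Chance of significance = P(|Z + bias/SE| > 1.96).

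| SD | SE | bias/SE | chance of p < 0.05 |
|---|---|---|---|
| 0.6 | 0.037 | 2.25 | 61% |
| 0.7 | 0.043 | 1.93 | 49% |
| 0.8 | 0.049 | 1.69 | 39% |

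At SD 0.7, a shift of 0.1 gives 12% and a shift of 0.4 gives 87% (77% to 95% over the SD range). A simulation with a 0.3 shift and a domain SD of 0.74 gave 58%. For a two-item surface domain the same 0.25 shift moves the average by 0.25/2 = 0.125.

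**Step 3: a source that needs no mistranslation.** Section 11 expects acquiescence and uses reverse scoring against it. With three items per domain the split is always 2:1: six domains have two reversed items and five have one. If one country agreed 0.25 points more with every item, a domain with two reversed items would move by (0.25 − 0.25 − 0.25)/3 = −0.083, and one with a single reversed item by +0.083. The result would look like a profile of barriers.

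**Step 4: size of the remedy's models.** Assume simple structure and freely correlated factors. One CFA then has 22 loadings + 33 error variances + 11 factor variances + 55 covariances = 121 parameters.
- Pooled model: 3,975/121 = 32.9 participants per parameter.
- Country models: 525/121 = 4.3; India 825/121 = 6.8.
- Seven groups, same structure, intercepts included: 7 × (121 + 33) = 1,078, or 3.7 per parameter.
- Equal loadings: 1,078 − 6 × 22 = 946, or 4.2.
- Equal intercepts, latent means freed in six groups: 946 − (6 × 33 − 6 × 11) = 814, or 4.9.

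**The case against.** The strongest reply is that the plan commits to little here. The country comparisons are exploratory, without pre-specified hypotheses, and Section 12b leaves their content open. The introduction's main purpose is to find the most common reasons, which ranks domains rather than countries. The SD and the shift are assumed, and Section 5c speaks of averages and confidence intervals rather than tests. All of this stands. It lowers the importance and makes 49% an illustration, not a property of this survey.

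A reader might infer several stronger things that the text does not support:
- That the plan fits only separate country models. The pooled model is the primary analysis.
- That country averages are explicitly planned for hand hygiene. Section 5c says so only for surface items; for hand hygiene it follows from Objective 4, the abstract and the scoring in Section 12b.
- That items will be removed or models revised country by country. The text permits this but does not state it, and the tolerance of 0.65 leans towards keeping the planned items.
- That all seven countries receive translated items. Section 11 does not say which do.

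The algebra in Step 1 is exact for a constant shift. On a bounded five-point item a real shift may also alter the variance slightly, but nothing in the plan would identify such a change as non-equivalence.

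None of these points supplies the missing check. Objective 4 still promises a comparison by domain and country, and no planned analysis shows that the scores are comparable.

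**Conclusion.** The concern holds, with moderate importance. Neither the pooled nor the separate country CFAs test equality of loadings and intercepts, and a constant shift in one item would pass both the country CFAs and the alpha check. Under the stated assumptions such a shift of 0.25 points makes a two-country comparison significant about 49% of the time (39% to 61%) instead of 5%. The figure depends heavily on the size of the shift, for which the documents hold no data. The point concerns how country differences are interpreted. It does not show that any item is in fact non-equivalent.

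**What to change.** In Section 12b:
- Require one common hand-hygiene item set for scoring, so that any item removed is removed in all countries.
- Add a multi-group CFA by country in AMOS, in sequence: same structure, then equal loadings, then equal intercepts, with the acceptance criterion stated in advance.
- Compare hand-hygiene domain averages between countries only where loadings and intercepts hold. Elsewhere, compare latent means with the non-equivalent items freed, or report by country without comparison.
- Report surface-disinfecting items by country descriptively. With at most two items per domain and no CFA, do not read differences in their averages as true country differences.

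The cost is wording and one further family of models, with no new data or software. Two downsides should be stated. Some domains may end with no country comparison. The seven-group models have about 4 to 5 participants per parameter, short of the 10 to 20 in Section 12a. The planned country models already share that shortfall, and the equality constraints ease it slightly.

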### 5. Hypothesis

#### 5a. Primary Hypothesis

The primary hypothesis relates to Objective 2.

The TDF determinates will describe the hand-hygiene data well.

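### At the planned sample sizes, chi-square/df below 2 and RMSEA of about 0.06 are conflicting limits on one statistic: the ratio means RMSEA below 0.016 for the primary pooled model and below 0.035 or 0.044 by country

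*Combined protocol and SAP*

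**What the plan says.** The primary hypothesis (section 5a) is "The TDF determinates will describe the hand-hygiene data well". Section 5b repeats the claim for each country or region as a secondary hypothesis.

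Section 12b supplies the only stated test of model fit; Cronbach's alpha there is a separate reliability step. On the order of analysis it says "The first models (the primary analyses) will be conducted with the data from all the countries", followed by models for each country. All of them are to be "tested for goodness of fit using three indices":

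- "absolute fit (based on a Chi-squared to degrees of freedom ratio, less than 2";
- "Root Mean Square Error of Approximation (RMSEA) of close to or less than 0.06";
- "comparative fit (based on an index 'close to' 0.95".

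The same cut-offs apply whatever the sample size. The text does not rank the indices, does not say whether all must be met, and does not say what follows if they disagree. It adds: "The models may be revised until the desired measures of fit are obtained".

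Table 2 (section 11) plans 375 mothers, 375 fathers and 75 teachers in India, and 225, 225 and 75 in each of six other countries.

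**The concern.** The chi-square/df ratio grows with N when a model has any real misfit, whereas RMSEA is scaled to remove N. Fixed limits on both can agree at only one sample size. Here the limits are applied to samples from 525 to 3,975, and the largest sample carries the primary hypothesis.

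Two things are at stake. First, a pooled model that meets the RMSEA criterion may miss the ratio only because the sample is large, and section 12b would then leave it open to re-specification. Second, the ratio can make the framework appear to hold within each country but not overall when the degree of misfit is the same throughout.

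**Working it through.** The plan gives no implied RMSEA, expected fit or power figure, so there is no stated result to reproduce.

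**Sample sizes (Table 2).** India: 375 + 375 + 75 = 825. Each other country: 225 + 225 + 75 = 525. Pooled: 825 + 6 × 525 = 3,975.

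**Conversion.** For one model per sample under the maximum-likelihood chi-square, RMSEA² = (χ²/df − 1)/(N − 1). At a ratio of 2, RMSEA = √(1/(N − 1)). At RMSEA 0.06, the ratio is 1 + 0.0036 × (N − 1).

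| Model | N | RMSEA at ratio 2 | Ratio at RMSEA 0.06 |
|---|---|---|---|
| Pooled (primary) | 3,975 | √(1/3974) = 0.0159 | 15.31 |
| India | 825 | √(1/824) = 0.0348 | 3.97 |
| Each other country | 525 | √(1/524) = 0.0437 | 2.89 |

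The two limits coincide at N = 1 + 1/0.0036 = 278.8, or about 279. Every planned model exceeds this, so the ratio is always the stricter limit: moderately so at 525, far more so when pooled. The degrees of freedom cancel in the conversion. Removing items under the alpha rule ("Items will be removed as necessary to achieve an alpha coefficient of 0.70 or above within each domain") therefore leaves these figures unchanged.

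**Shortfall in recruitment.** Section 11 closes a country's survey at 30 days even if its target is not met. At 75% of target the ratio's implied RMSEA limits become 0.018 / 0.040 / 0.051 (pooled / India / each other country). At 50% they become 0.022 / 0.049 / 0.062.

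**Illustration of pass probabilities.** Assume 11 correlated factors with simple structure and the 33 hand-hygiene items of Appendix A. There are 33 × 34/2 = 561 moments and 33 + 33 + 55 = 121 parameters, so df = 440. Assume also the same true RMSEA in every model and the initial, unrevised model. Then P(ratio < 2) is the noncentral chi-square probability below 2 × df, with noncentrality (N − 1) × df × RMSEA².

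| True RMSEA | Pooled | India | Each other country |
|---|---|---|---|
| 0.016 | 0.45 | 1.00 | 1.00 |
| 0.018 | 0.01 | 1.00 | 1.00 |
| 0.02 | 0.00 | 1.00 | 1.00 |
| 0.03 | 0.00 | 0.99 | 1.00 |
| 0.035 | 0.00 | 0.47 | 1.00 |
| 0.04 | 0.00 | 0.005 | 0.93 |
| 0.05 | 0.00 | 0.00 | 0.006 |

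At every value in this table the sample RMSEA is at or below 0.06 with probability 1.00 in all models. From about 0.018 to 0.03 the pooled model almost surely misses the ratio while the country models pass it; with independent samples all seven countries pass together with probability 0.99 at 0.03. With 22 items (253 − 99 = 154 df) this range narrows slightly, to 0.0184 to 0.0292.

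**The case against.** The strongest reply is that section 12b lists three facets of fit and then speaks of the desired measures in the plural, so the natural reading is that all three are sought. A reader might infer from the missing combining rule that the plan can give no definite verdict. That goes too far: on the all-required reading the verdict is definite, because the ratio decides between these two indices. What stands is that this reading makes the 0.06 limit redundant at every planned N and holds the primary model to an RMSEA below 0.016, which the plan neither states nor justifies.

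A second inference would be that a model missing the ratio is declared not to fit, and that one meeting RMSEA 0.06 would be declared to fit if RMSEA governed. Neither follows. Missing the ratio first opens the model to revision, so the probabilities above describe the initial model and not the plan's final conclusion. Comparative fit must also be considered: the documents give no loadings or correlations from which to predict it, and it could fail when RMSEA is small.

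A third inference would be that a failure of the pooled model alone must be an artefact of N. Pooling seven countries, translated items and separate parent and teacher wordings may add real misfit. Such a failure could reflect N, heterogeneity or both, and the ratio cannot separate them.

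Finally, the probabilities rely on the noncentral chi-square holding for 5-point items, and one pooled model is inferred from the text. If parents and teachers were modelled separately, the pooled limits would be 0.017 for parents (3,450) and 0.044 for teachers (525). The conflict would remain, but the teachers' limit would be far less strict.

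**Conclusion.** The concern holds and should be fixed. As written, section 12b places two conflicting limits on what is, under maximum likelihood, a single statistic, and the conflict is widest for the primary analysis. Either the ratio silently sets a standard that tightens with N, or the governing index is unstated.

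The conversions rest on the maximum-likelihood chi-square, one model per sample and Table 2 being filled. The contrast between pooled and country models rests further on equal true misfit and df of 440, and is an illustration only. The documents give no expected RMSEA, so whether results will fall in the affected range is unknown.

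**What to change.** In section 12b, state that chi-square, df and their ratio are reported descriptively and serve neither as a pass/fail criterion nor as a reason to revise a model. State that fit of the pooled and country models is judged on the RMSEA (with its 90% CI) and comparative-fit criteria already planned, both required.

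The cost is one or two sentences; no new data are needed, and both indices are already in the plan. The downside is that the pooled claim loses its strictest criterion: on RMSEA alone, a ratio of up to 15.3 would be acceptable. The fit of the unrevised model should therefore be reported alongside that of any revised model.

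If the sponsor prefers to keep the ratio as a criterion, section 12b should say how the indices combine and acknowledge the RMSEA limits that the ratio implies at each N. Replacing the approximate wording of the other two cut-offs with exact values is optional. The clause allowing revision until fit is reached is a separate issue that this change does not settle.
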